### 4.4.2 Handling of Missing Values/Censoring/Discontinuations

Missing data will not be imputed. Values that are below the limit of quantification (LOQ) will be replaced by LOQ/2 for treatment group and be replaced by 0 for placebo group.

## 4.5 Analysis of Secondary Objective

The secondary objective is to evaluate the relative exposure of diclofenac in the knee joint vs. plasma.

### 4.5.1 Secondary Endpoints

The secondary endpoints are

- Ratio between diclofenac concentration in treated knee synovial tissue and diclofenac plasma concentration (sample taken during surgery) after 7 days topical application of study treatment to the knee (12 hours after last application)
- Ratio between diclofenac concentration in treated knee synovial fluid and diclofenac plasma concentration (sample taken during surgery) after 7 days topical application of study treatment to the knee (12 hours after last application)

Following the same approach as for the primary endpoints, the ratios between diclofenac concentration in synovial tissue / fluid and diclofenac plasma concentration (last sample taken during surgery) will be summarized descriptively by treatment group in both the arithmetic and the logarithmic scale. Geometric means will be calculated with two-sided 95% confidence intervals (Table 14.2.4.1 and Table 14.2.5.1). Boxplots for study treatment group will be produced (Figure 14.2.5 and Figure 14.2.7). The analyses will be performed on the analysable population.

### 4.5.2 Handling of Missing Values/Censoring/Discontinuations

Missing data will not be imputed. For diclofenac concentrations in treated knee synovial tissue or synovial fluid that are below the limit of quantification (LOQ), refer to Section 4.4.2 for imputation. For diclofenac plasma concentrations that are below the limit of quantification (LOQ), refer to Section 4.8.2 for imputation. For placebo group the ratios will be set as missing.

## 4.6 Analysis of Exploratory Objectives

The exploratory objectives are

- To evaluate treatment effects upon COX-2 inhibition in the knee joint
- To evaluate treatment effects upon inflammatory cytokines in the knee joint

### 4.6.1 Exploratory Endpoints

The exploratory endpoints are

GlaxoSmithKline Consumer Healthcare Confidential Page 17 of 22

- PGE2 levels in treated knee synovial tissue and synovial fluid after 7 days topical administration to the knee (12 hours after last application)
- IL-6 and TNF $\alpha$  levels in treated knee synovial tissue and synovial fluid after 7 days topical administration to the knee (12 hours after last application)

The success criteria for exploratory objectives are

- diclofenac reduces PGE2 levels in treated knee synovial tissue or synovial fluid after 7 days topical administration to the knee compared to placebo gel
- diclofenac reduces levels of inflammatory cytokines i.e. TNFα and/or IL-6 associated with OA in treated knee synovial tissue or synovial fluid after 7 days topical administration to the knee compared to placebo gel

 $PGE_2$  and inflammatory cytokines levels will be summarized descriptively in both the arithmetic and the logarithmic scale (Table 14.2.6 - Table 14.2.11). The mean, SD, min, P10, Q1, median, Q3, P90 and max will be summarized.

For each endpoint, the success criterion will be addressed by a two-sided test for superiority at level alpha=0.05 in an exploratory manner. Log-transformed mean levels will be compared between treatment groups using an analysis of variance including treatment as a fixed effect. The two-sided 95% confidence interval for the ratio of geometric means on the original scale will be derived by back-transforming the confidence interval for the difference between treatment groups on the log-transformed scale obtained from the analysis.

The analyses will be performed on the analysable population.

The analyses will be repeated for the PP-PD (Per Protocol Pharmacodynamic) Population (Table 14.2.13 - Table 14.2.18).

### 4.6.2 Handling of Missing Values/Censoring/Discontinuations

Missing data will not be imputed. Values that are below the limit of quantification (LOQ) will be replaced by LOQ/2.

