#### 10.2.9 Handling of Dropouts and Missing Data

Missing data will not be imputed. All evaluable parameters after 7 days from subjects in the analysable population will be used in the analysis of primary, secondary and exploratory endpoints. Values that are below the limit of quantification (BLOQ) will be replaced by LOQ/2.

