### 3.2 Centers Pools

This study is a multicenter study. Data will be summarized for all centers combined. Statistical analyses will not be adjusted for centers.

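### Below-LOQ biomarker values set to LOQ/2 and analysed as measurements can bias the between-arm ratio of geometric means in either direction and make its 95% CI undercover; add below-LOQ counts and a censored-regression sensitivity analysis

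*SAP*

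**What the plan says.** The substitution rule for the three biomarkers is in SAP 4.6.2: "Values that are below the limit of quantification (LOQ) will be replaced by LOQ/2". Protocol 10.2.9 has the same rule for all assays ("Values that are below the limit of quantification (BLOQ) will be replaced by LOQ/2"). SAP Table 5-1 changes it for some diclofenac values and restates LOQ/2 for the biomarkers.

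The analysis is in SAP 4.6.1: "Log-transformed mean levels will be compared between treatment groups using an analysis of variance including treatment as a fixed effect". The test is a "two-sided test for superiority at level alpha=0.05 in an exploratory manner". The interval for the ratio of geometric means "will be derived by back-transforming the confidence interval for the difference between treatment groups on the log-transformed scale". Treatment is the only model term (SAP 3.2: "Statistical analyses will not be adjusted for centers").

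For the biomarker tables, SAP 4.6.1 specifies: "The mean, SD, min, P10, Q1, median, Q3, P90 and max will be summarized". It lists no count or share below LOQ. For diclofenac in synovial tissue and fluid, by contrast, SAP 4.4.1.2 asks for the proportion above LOQ with a Wilson interval.

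The only repeat of the biomarker analysis is in the PP-PD population, and no different LOQ rule is stated for it. Neither document gives a biomarker LOQ, a log-scale SD, an expected effect or an expected share below LOQ.

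**The concern.** A value below LOQ is left-censored: it is known only to lie somewhere under the limit. Replacing all such values by one constant makes a guess about where they lie, and the ANOVA then treats the guess as data. If the gel lowers a biomarker, more active than placebo values fall under the limit. The guess therefore carries more weight in the active arm, and its error does not cancel between arms.

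At stake is the ratio of geometric means and its CI. The placebo arm was included for bioactivity comparisons (Protocol section 3, SAP 1.3), and these ratios are the only between-arm effect estimates in the plan. Without the below-LOQ share by arm, a reader cannot readily judge the size or even the direction of the error.

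**Working it through.** **Inputs from the documents.** About 30 active and 15 placebo evaluable (SAP 1.4), from about 50 randomised with 10% dropout: 45/(1 - 0.10) = 50, which reproduces the plan's figure. Two-sided alpha 0.05; ANOVA on logs with treatment only; LOQ/2 in both arms. The plan has no figure for bias, coverage or below-LOQ share to reproduce.

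**Assumptions.** Log-normal data, equal SD in both arms, one LOQ per assay. True ratios 1.0, 0.7, 0.5 and 0.3; natural-log SD 0.4, 0.7, 1.0 and 1.5; placebo share below LOQ 0 to 70%.

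**Expected ratio in closed form.** Let log values be normal with mean m and SD s, L = ln(LOQ), z = (L - m)/s, p = Φ(z). After substitution the arm mean is

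E = p(L - ln 2) + (1 - p)m + sφ(z),

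and the ANOVA ratio estimates exp(E_active - E_placebo). Take m = 0 on placebo and m = ln 0.5 = -0.693 on active.

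- *s = 1.0, 50% of placebo below LOQ.* L = 0. Placebo: 0.5(-0.693) + 0 + 0.399 = 0.052. Active: z = 0.693, p = 0.756, φ = 0.314, so E = 0.756(-0.693) + 0.244(-0.693) + 0.314 = -0.379. Ratio = exp(-0.379 - 0.052) = **0.65** against a true 0.50.
- *s = 0.4, 10% of placebo below LOQ.* L = -0.513. Placebo: 0.1(-1.206) + 0 + 0.4(0.1755) = -0.050. Active: z = 0.451, p = 0.674, φ = 0.360, so E = 0.674(-1.206) + 0.326(-0.693) + 0.4(0.360) = -0.895. Ratio = exp(-0.895 + 0.050) = **0.43**.

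The direction follows from where the censored values really lie. LOQ/2 is 0.69 below ln(LOQ). The true mean of the censored values lies m - sφ(z)/p - L from ln(LOQ). In the first case that is 0.80 below it on placebo and 1.11 below it on active, so the constant is too high, mostly on active, and the effect shrinks. In the second it is 0.19 and 0.39 below, so the constant is too low, mostly on active, and the effect is exaggerated.

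**Simulation of the planned analysis.** n = 30 vs 15, pooled variance, t(43), 20,000 runs per cell, true ratio 0.50:

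| log-SD | placebo / active below LOQ | ratio | CI coverage |
|---|---|---|---|
| 0.4 | 5% / 53.5% | 0.423 | 82.0% |
| 0.4 | 10% / 67.4% | 0.430 | 80.2% |
| 0.4 | 30% / 88.7% | 0.512 | 88.4% |
| 0.4 | 50% / 95.8% | 0.625 | 47.6% |
| 0.7 | 10% / 38.5% | 0.480 | 94.5% |
| 0.7 | 50% / 83.9% | 0.636 | 66.0% |
| 1.0 | 10% / 27.8% | 0.500 | 94.6% |
| 1.0 | 30% / 56.7% | 0.561 | 91.8% |
| 1.0 | 50% / 75.6% | 0.649 | 74.9% |
| 1.5 | 10% / 20.6% | 0.515 | 94.7% |
| 1.5 | 50% / 67.8% | 0.667 | 82.0% |

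**Other effects, log-SD 1.0, 50% of placebo below LOQ.** True 0.30 gives 0.54 with 19.2% coverage. True 0.70 gives 0.78 with 91.5%.

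**No effect (true 1.0).** The ratio stays at 1.00, coverage is 94.7 to 95.5% and type I error 4.5 to 5.3% in every cell.

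**Comparator.** Left-censored normal maximum likelihood on the log scale, 600 runs per cell, true ratio 0.50:

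- SD 1.0 at 10/30/50% of placebo below LOQ: 0.50/0.51/0.50, coverage 95.0/95.3/96.2%.
- SD 1.5 at 50%: 0.49, 94.2%.
- SD 0.7 at 50%: 0.51, 93.8%, with 5 of 600 runs unusable.
- SD 0.4 at 10%: 0.50, 95.8%.
- SD 0.4 at 30%: 0.51, 92.3%, with 15 of 600 unusable.

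**The case against.** The strongest reply is that the harm is conditional. Nothing in the documents says that heavy censoring is expected, and the worst figures need about half of the placebo values below LOQ or an unusually small spread. That stands, and it is why the point asks for an added analysis and not a replaced one.

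Second, the rule was prespecified in the protocol and repeated in the SAP, the comparison is labelled exploratory, and study success is detection of diclofenac in the joint. All true. A reader might infer that the success criterion or the diclofenac summaries are at risk from this rule; they do not depend on the biomarker analysis.

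Third, censoring is not wholly hidden. If the tabulated minimum, P10, Q1 or median equals LOQ/2, the reader learns that at least about 10%, 25% or 50% of values were replaced. This is partly right, but it gives coarse lower bounds where a count would be exact.

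Three stronger readings are tempting and do not hold. The ratio does not always shrink toward 1, as the log-SD 0.4 cells show. A small placebo share is not always harmless: 5-10% is enough to matter at log-SD 0.4, and the documents give no SD that would exclude this. The rule does not create false positives, because with no treatment effect the substitution error is the same in both arms.

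**Conclusion.** The point holds in conditional form. Given a real treatment effect and a material share of values below LOQ, LOQ/2 substitution biases the reported ratio and its nominal 95% CI undercovers. For a true ratio of 0.50 with half of placebo below LOQ, the ratio is about 0.64 to 0.67 and coverage 66 to 82% over log-SD 0.7 to 1.5. With log-SD 0.4 and 5-10% of placebo below LOQ, the reduction is exaggerated, with coverage about 80%. With log-SD 0.7 or more and at most 10% of placebo below LOQ, the error is at most about 0.03 on the ratio and coverage is about 93 to 95%.

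All of this rests on assumed SDs, effects and below-LOQ shares, on log-normality and on equal SDs, so no single figure can be attached to this trial. It is a cheap improvement to an exploratory estimate, not a threat to the study's main conclusion.

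**What to change.** In SAP 4.6.1 and 4.6.2:

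1. Add n (%) below LOQ by arm to Tables 14.2.6-14.2.11 and, for PP-PD, 14.2.13-14.2.18.
2. Keep the planned ANOVA. For any endpoint with below-LOQ values, add a prespecified sensitivity analysis: one left-censored log-normal regression with the same treatment term (for example SAS PROC LIFEREG). Take the ratio, 95% CI and p-value all from that model, so that interval and test agree. State that it guides interpretation of effect size when the two analyses differ materially.
3. Where that model cannot be fitted reliably, report the proportion above LOQ by arm with the Wilson interval already used for diclofenac, and say that the ratio is not reliable. A fixed cut-off such as 80% below LOQ in an arm is best avoided: at log-SD 0.7 with 50% of placebo below LOQ, the expected active share is already 84%, and such a rule would withdraw the ratio in about two thirds of trials.

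The cost is one table row and a few lines of code. The statistical price is clearly wider intervals under heavy censoring (about 1.7 times the log-scale width at 50% of placebo below LOQ), reliance on log-normality, which the geometric-mean analysis already leans on, and an occasional unusable fit.

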## 4.7 Analysis of Safety

### 4.7.1 Adverse Events and Serious Adverse Events

Adverse events (AEs) will be summarized (Table 14.3.1.1) by presenting, for each treatment group, the number and percentage of subjects having any AE, any Treatment Emergent adverse events (TEAE), any serious TEAE, any study drug-related TEAE, any study drug-related serious TEAE, any TEAE leading to treatment discontinuation or study discontinuation, or any AE leading to death. TEAE is defined as an AE that starts on or after the date of first study treatment. For an AE with an incomplete start date where the day is missing while the year and month are present and the same as the date of first study treatment administration, the date of first study treatment will be assumed to be the AE start date.

TEAEs will be summarized by presenting, for each treatment group, the number and percentage of subjects having any TEAE, any TEAE in each MedDRA primary system organ class (SOC) and having each individual TEAE (using MedDRA preferred term).

This will be done separately for all TEAEs by SOC/Preferred term (Table 14.3.1.2) and for TEAEs that are suspected to be drug-related by SOC/Preferred term (Table 14.3.1.4). All TEAEs will also be tabulated in corresponding fashion by SOC/Preferred term/Intensity (Table 14.3.1.3 and Table 14.3.1.5). Any other information collected (e.g. action taken, duration, outcome, seriousness) will be listed as appropriate.

Additionally, all adverse events will be listed (listing 16.2.7.1).

Deaths occurring during treatment (if any) will be listed by treatment, including the date and study day of death, and the principal cause of death (listing 14.3.2.1). Non-fatal serious AEs and TEAEs leading to study treatment discontinuation will be listed (listing 14.3.2.2 and Listing 14.3.2.3).

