The first dose of the study treatment is applied to the target knee during Visit 2 on Day 1 by a study nurse (or designee) at the study site. It will then be applied twice a day by a trained nurse (or designee) at the subject's home or other place of convenience commencing on the evening of Day 1 to allow for directly observed compliance, a record of drug applied and a check for concomitant medications and AEs. Subjects will be admitted to the unit on the day before the scheduled surgery (Day 7). The last dose of study treatment will be administered at the study site 12 hours (window -1/+3 hrs) prior to arthroplasty surgery. Additional activities/procedures may be required in the undertaking of the arthroplasty. Unless they fall within the details of this protocol, laboratory manual or pharmacy manual, they are outside the scope of this study.

Blood samples to measure diclofenac plasma concentrations will be taken as follows:

- One blood sample at baseline within one hour prior to administration of study treatment (Visit 2/Day 1)
- One blood sample within one hour prior to last dose of study treatment (Visit 3/Day 7)
- One blood sample between last dose of study treatment and commencement of surgery (at least 3 hours after dosing and more than 3 hours before surgery)
- One blood sample during surgery on Day 8 (between anaesthesia and completion of surgery)

The subjects will have a scheduled arthroplasty performed on their target knee (upon which the study treatment has been applied). During the surgical intervention synovial tissue and synovial fluid will be sampled as follows:

- Two (2) synovial tissue samples of approximately 2 to 3 cm^3 each
- Four (4) aliquots of 2.5-3 mL of synovial fluid

The surgical procedure will be performed according to the site's standard process. Sampling of the tissue and fluid will occur using clean equipment not used previously for surgery. This is to avoid contamination of the samples with blood. All sample handling details will be described in the Laboratory Study Manual.

The following safety assessments will be conducted:

- Complete physical examination and vital signs at all study center visits.
- Electrocardiogram: 12-lead ECG at Screening visit, Pre-surgery visit and Final visit
- Standard clinical safety laboratory (biochemistry and hematology) at Screening visit, Presurgery and at Final visit
- AEs at all study visits and nurse's home visits

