### 5.5 Administration

The study treatment will be applied twice a day for seven days. The first and last dose of study treatment will be applied by a trained study nurse at the study site. The doses in between first and last dose will be applied by a trained study nurse at the subject's home or at a place convenient for the subject.

A 4 gram dose, measured with a dosing card, will be applied over a 400 cm^2 surface of the knee identified for treatment (target knee). The area will be identified and recorded using a derm pen and a stencil before the first dose to permit consistent redosing at the same site. The nursing staff will undergo training to ensure dosing can be done in a consistent manner.

The study nurse, wearing gloves, will spread a dose of study treatment, measured using a dosing card, on the subject's target knee. The study treatment should be rubbed gently into the skin for about 1 minute over a region of approximately 400 cm^2 per knee (i.e., about the surface of the two palms of the hands). Doses should be applied at intervals as close as possible to every 12 hours.

The treated area must not be covered within the first 10 minutes or washed, bathed, or showered within the first three (3) hours after the application.

The application site should not be occluded. The use of heat or heat pad on the target knee is not allowed.

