#### 6.2.3 Pre-Surgery Day 7 and Surgery Day 8 (Visit 3)

The subject will be admitted to the study site in the afternoon of Day 7 and remain at the study site until discharge post-surgery. The surgery will take place in the morning of Day 8, 12 hours (window -1/+3 hrs) after last dose of study treatment.

The surgery may be delayed by up to 7 days, in which case the study treatment will continue to be applied twice daily up to 14 days. If the surgery is delayed by more than 7 days, the subject should be withdrawn from the study. Subject Withdrawal/Early Termination assessments will be conducted (See Section 6.4 Subject Withdrawal). No further PK blood samples will be collected and the rescheduled surgery will not be part of the study.

On Day 7 (pre-surgery), the following procedures will be completed and results recorded in source documents:

- Collect all returned study treatment
- Collect all returned rescue medication
- Review concomitant medications
- Review any AEs (continuing up to surgery)
- Collect a blood sample for pharmacokinetic analysis within 1 hour prior to last dosing.
- Dose subject with final dose of study treatment (12 hours (window -1/+3 hrs) prior to surgery)

**After dosing**, (ie. Between final dosing with study treatment and prior to surgery) the following procedures will be completed:

- Conduct physical examination and collect vital signs (BP, PR, RR, temperature)
- Collect standard 12-lead ECG measurements
- Following at least a 4 hour fast, collect blood and urine specimens for safety laboratory tests
- Collect one blood sample for diclofenac levels —at least 3 hours after dosing and more than 3 hours before surgery
- The subject will be prepared for surgery according to the procedures of the surgical center; if shaving of the knee area is required, this should occur as close as possible to the surgery but in any event no less than 3 hours after dosing

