#### 6.3 Follow-up Visit (Visit 4) Day 8-10

The follow up Visit will take place after the surgery prior to discharge of the subject from the surgical center.

At this visit the following procedure will be conducted and results recorded in the source documents.

- Conduct physical examination and collect vital signs.
- Standard 12-lead ECG.
- Following at least a 4-hour fast, collect blood and urine specimens for safety laboratory tests
- Review concomitant medications
- Record any AEs
- The subject will be discharged from the study

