#### 8.2 Reporting Period

#### 8.2.1 Adverse Event

AEs (serious and nonserious) will be collected from the time the subject has signed informed consent and until 28 days following last administration of the investigational product.

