#### 10.2.7 Safety Analysis(es)

Safety variables will be summarized on the safety population.

Exposure to study drug (number of applications, total weight of gel used) will be summarized by treatment group.

Treatment Emergent adverse events (TEAE, i.e. AEs that start or worsen after first study treatment administration) will be summarized by presenting, for each treatment group, the number and percentage of subjects having any TEAE, any TEAE in each MedDRA primary System Organ Class (SOC) and having each individual TEAE (using MedDRA preferred term). This will be done separately for all TEAEs and for TEAEs that are suspected to be drug-related. All TEAEs will also be tabulated in corresponding fashion by severity. Any other information collected (e.g. action taken, duration, outcome, seriousness) will be listed as appropriate.

All adverse events (prior to treatment and treatment emergent) will be listed.

Chemistry and hematology results at screening, Visit 3 and at Visit 4 will be summarized by the mean, standard deviation, median, minimum and maximum values in each treatment group. Shift tables (between baseline and Visit 3, between Visit 3 and Visit 4) will also be presented. Laboratory normal ranges and all laboratory test results will be listed.

Vital signs (systolic and diastolic blood pressure, pulse rate, respiratory rate) recorded at Visit 3 and changes in vital signs from Visit 2 (baseline) to Visit 3 will be summarized by the mean,

GlaxoSmithKline Consumer Healthcare Confidential Template Version Effective: 22-Jun-2017 Page **61** of **71** 

standard deviation, median, minimum and maximum values in each treatment group. Vital signs at each assessment will also be listed.

ECG results at Visit 3 and Visit 4 will be summarised.

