### 4.7.3 Vital Signs

Vital signs (systolic and diastolic blood pressure, pulse rate, respiratory rate, body temperature) recorded at Visit 3 and changes in vital signs from Visit 2 (Baseline) to Visit 3 will be summarized by the mean, standard deviation, median, minimum and maximum values in each treatment group (Tables 14.3.6). Vital signs at each assessment will also be listed (Listing 16.2.9.1).

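### TEAE tables run from first gel with no split at surgery, so post-arthroplasty events common to both arms dilute the descriptive gel-versus-placebo comparison

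*SAP*

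**What the plan says.** SAP 4.7.1 gives the rule: "TEAE is defined as an AE that starts on or after the date of first study treatment". Protocol 10.2.7 words it as "AEs that start or worsen after first study treatment administration". Neither text ends the window or cuts it at surgery.

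Gel exposure is short: "The study treatment will be applied twice a day for seven days" (protocol 5.5), with up to 14 days allowed if surgery is delayed. Surgery follows closely: "The surgery will take place in the morning of Day 8, 12 hours (window -1/+3 hrs) after last dose of study treatment" (protocol 6.2.3). AEs are collected "until 28 days following last administration of the investigational product" (protocol 8.2.1), so nearly all of that tail is post-operative. The last scheduled contact comes much sooner: "The follow up Visit will take place after the surgery prior to discharge of the subject from the surgical center" (protocol 6.3, Day 8 to 10).

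SAP 4.7.1 plans by-arm summaries of any TEAE, serious TEAEs, drug-related TEAEs and TEAEs leading to discontinuation (Table 14.3.1.1). It also plans tables by system organ class and preferred term, by intensity, and for drug-related events (Tables 14.3.1.2 to 14.3.1.5). None is split by period. Other safety data are reported by visit. Vital signs are those "recorded at Visit 3 and changes in vital signs from Visit 2 (Baseline) to Visit 3" (SAP 4.7.3), and laboratory shifts are tabulated from baseline to Visit 3 and from Visit 3 to Visit 4 (SAP 4.7.2). The schedule of activities places the Visit 3 safety assessments after the final dose and before surgery.

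**The concern.** Protocol 1.2 presents arthroplasty as a model for measuring exposure in the joint, and says the gel is not indicated for severe OA. Surgery is how the samples are obtained; it is not part of how the product is used. After surgery each subject has had anaesthesia and receives analgesia by the center's own procedures. The NSAID restriction in protocol 5.8 runs only to completion of surgery, so post-operative events reflect several exposures other than the study gel.

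When these events share a row with those that arose during dosing, a reader cannot tell from the row how many subjects had an event while on gel. A real difference during dosing would look smaller, and the any-TEAE percentage could be taken as a property of a topical gel when part of it belongs to the operation. At stake is how readable the safety summary is. The primary and secondary results are not affected.

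**Working it through.** **The plan's own figure.** Protocol 10.1 and SAP 1.4 allow 10% dropout to keep 45 evaluable: 45 / (1 − 0.10) = 50, which reproduces. At 2:1 this is 50 × 2/3 = 33.3 and 50 × 1/3 = 16.7, so about 33 active and 17 placebo. The documents state no AE rate, AE test or AE power, so there is no further figure to reproduce.

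**How much of the window is post-operative.** Share = post-surgery days / (gel days + post-surgery days), ignoring the 12 hours between last gel and surgery.
- 7 gel days, full 28-day collection: 28/35 = 80%.
- 14 gel days, full 28-day collection: 28/42 = 67%.
- 7 gel days, capture ending in practice at Visit 4, 1 to 3 days later: 1/8 = 12.5% to 3/10 = 30%.

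**Dilution in the any-TEAE row.** Let g be the gel-period risk in an arm and s the post-surgical AE risk, the same in both arms and independent of g. Then

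any-TEAE risk = 1 − (1 − g)(1 − s), and the difference between arms = (g_active − g_placebo)(1 − s).

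All values of g and s below are assumptions. For g = 25% v 10% and s = 20%, active is 1 − 0.75 × 0.80 = 40% and placebo is 1 − 0.90 × 0.80 = 28%, a difference of 0.15 × 0.80 = 12 points.

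| s | Active | Placebo | Difference | Ratio | Power, 33 v 17 |
|---|---|---|---|---|---|
| 0% (pre-surgery column) | 25% | 10% | 15 points | 2.50 | 21% |
| 20% | 40% | 28% | 12 points | 1.43 | 12% |
| 40% | 55% | 46% | 9 points | 1.20 | 9% |
| 60% | 70% | 64% | 6 points | 1.09 | 7% |
| 80% | 85% | 82% | 3 points | 1.04 | 5% |

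With a larger assumed gel effect, 40% v 10%, the difference falls from 30 points to 24, 18, 12 and 6 over the same values of s, and power falls from 61% to 36%, 23%, 15% and 9%. Power is the two-sided 5% normal approximation. Fisher's exact test gives 16% and 54% for the two undiluted cases. The plan tests none of these rows; power is shown only to indicate how little the numbers can resolve, even with a split.

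**Partial dates.** SAP 4.7.1 sets an AE with a missing day, in the same month as first treatment, to the date of first treatment. Where Day 1 and Day 8 fall in the same month, a post-operative event of that month would be dated to Day 1. This does no harm to a single TEAE count, but it would put the event in the wrong column of a table by period.

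**The case against.** A reader might infer that surgical events swamp any gel effect, or that the AE tables cannot show tolerability at all. The documents do not support either reading.

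- Protocol 8.1.1 excludes expected signs, symptoms and laboratory findings of the scheduled surgery unless they are worse than expected. Much routine post-operative experience should therefore never be an AE. Complications during the hospital stay are AEs (protocol 8.1.2), so the background is lowered but not removed.
- No post-surgical AE rate is given. At an assumed 20%, 12 of 15 points survive.
- Preferred-term rows are diluted only where surgery produces the same term. A skin reaction to the gel would largely keep its contrast, and rash after application is a listed reason for discontinuation (protocol 6.4).
- Drug-related TEAEs have their own tables. Causality is judged by investigators blind to arm who must weigh timing and alternative causes (protocol 5.1, 8.4.2). It remains a judgement, and a hard one around surgery, but it is aimed at the right question.
- The 28-day tail may be thinly captured: no visit follows Visit 4, and protocol 8.7 does not oblige investigators to seek AEs actively in former subjects.
- Laboratory and vital-sign summaries follow scheduled visits; nothing says they were designed to separate surgery from gel.
- The study has no safety objective, the AE tables are descriptive, and about 33 v 17 subjects can resolve little even after a split.

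All of this stands and limits the point. It does not answer the narrower one: the any-TEAE, serious-TEAE, system organ class and intensity rows still mix the two periods, and no by-arm summary shows the gel period alone.

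**Conclusion.** The point holds as one of dilution and readability. The pooled rows combine gel-period and post-operative events, and post-operative events with the same risk in both arms shrink any contrast by the factor (1 − s). Under the assumed 25% v 10%, that takes 15 points to between 12 and 3 as s runs from 20% to 80%. The true size cannot be fixed from the documents. The result rests on s being equal across arms and independent of gel-period events.

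A reader might also infer that the arms are compared unfairly. They are not: allocation is randomized within center and surgery comes to both arms alike, so this is not between-arm bias. Nor would the split make the comparison well powered. Its value is that gel-period rates can be read directly.

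**What to change.** In SAP 4.7.1, keep the TEAE tables over the whole period and add onset-period columns to Tables 14.3.1.1 to 14.3.1.5: (a) first application to before surgery, and (b) surgery onward.

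- **Assignment.** Use AE onset date against surgery date. The documents mention an onset date but no clock time, so place surgery-date events in (b) unless the record shows onset before surgery, and flag them in Listing 16.2.7.1. The flag matters because a reaction to the last application could begin on the morning of surgery.
- **Partial dates.** Do not let the missing-day rule put events in (a) by default. Report them as period unknown, or classify them at the blind data review.
- **Interpretation.** Describe gel tolerability from (a) alongside the overall and drug-related tables. Do not rely on (a) alone, since a gel effect may appear after surgery.

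The cost is SAP wording and programming on dates the study already needs. The downside is longer tables with small counts.
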